3.6 Treatment of Infusion Reactions

All Grade 3 or 4 infusion reactions should be reported within 24 hours to the BMS Medical Monitor and reported as an SAE if criteria are met. Infusion reactions should be graded according to NCI CTCAE (v4.03) guidelines.

Of note, since nivolumab contains only human immunoglobulin protein sequences, it is unlikely to be immunogenic and induce infusion or hypersensitivity reactions. However, if such a reaction were to occur, it might manifest with fever, chills, rigors, headache, rash, pruritus, arthralgia, hypotension, hypertension, bronchospasm, or other symptoms.

Treatment recommendations applicable for all study drugs are provided below and may be modified based on local treatment standards and guidelines as appropriate:

For Grade 1 symptoms: (Mild reaction; infusion interruption not indicated; intervention not indicated)

Remain at bedside and monitor subject until recovery from symptoms. The following prophylactic premedications are recommended for future infusions: diphenhydramine 50 mg (or equivalent) and/or paracetamol 325 to 1000 mg (acetaminophen) at least 30 minutes before additional nivolumab administrations.

For Grade 2 symptoms: (Moderate reaction requires therapy or infusion interruption but responds promptly to symptomatic treatment [eg, antihistamines, non-steroidal anti-inflammatory drugs, narcotics, corticosteroids, bronchodilators, IV fluids]; prophylactic medications indicated for ≤ 24 hours).

Stop the nivolumab infusion, begin an IV infusion of normal saline, and treat the subject with diphenhydramine 50 mg IV (or equivalent) and/or paracetamol 325 to 1000 mg (acetaminophen); remain at bedside and monitor subject until resolution of symptoms. Corticosteroid or bronchodilator therapy may also be administered as appropriate. If the infusion is interrupted, then restart the infusion at 50% of the original infusion rate when symptoms resolve; if no further complications ensue after 30 minutes, the rate may be increased to 100% of the original infusion rate. Monitor subject closely. If symptoms recur then no further nivolumab will be administered at that visit. Administer diphenhydramine 50 mg IV, and remain at bedside and monitor the subject until resolution of symptoms. The amount of study drug infused must be recorded on the electronic case report form (eCRF). The following prophylactic premedications are recommended for future infusions: diphenhydramine 50 mg (or equivalent) and/or paracetamol 325 to 1000 mg (acetaminophen) should be administered at least 30 minutes before additional nivolumab administrations. If necessary, corticosteroids (recommended dose: up to 25 mg of IV hydrocortisone or equivalent) may be used.

For Grade 3 or Grade 4 symptoms: (Severe reaction, Grade 3: prolonged [ie, not rapidly responsive to symptomatic medication and/or brief interruption of infusion]; recurrence of symptoms following initial improvement; hospitalization indicated for other clinical sequelae [eg, renal impairment, pulmonary infiltrates]). Grade 4: (life threatening; pressor or ventilatory support indicated).

Immediately discontinue infusion of nivolumab. Begin an IV infusion of normal saline, and treat the subject as follows. Recommend bronchodilators, epinephrine 0.2 to 1 mg of a 1:1,000 solution for subcutaneous administration or 0.1 to 0.25 mg of a 1:10,000 solution injected slowly for IV administration, and/or diphenhydramine 50 mg IV with methylprednisolone 100 mg IV (or equivalent), as needed. Subject should be monitored until the investigator is comfortable that the symptoms will not recur. Nivolumab will be permanently discontinued. Investigators should follow their institutional guidelines for the treatment of anaphylaxis. Remain at bedside and monitor subject until recovery from symptoms. In the case of late-occurring hypersensitivity symptoms (eg, appearance of a localized or generalized pruritus within 1 week after treatment), symptomatic treatment may be given (eg, oral antihistamine, or corticosteroids).

If any vital sign is abnormal at the final check, the subject must be observed further for a period of time, as clinically indicated.

The start and stop time of the study drug infusion should be documented. If there are any new or worsening clinically significant changes since the last examination, report changes on the appropriate non-serious or SAE page.

When slowing or restarting an infusion due to an infusion reaction, vital signs should be monitored every 15 minutes (± 5 minutes) or as directed by the investigator until the infusion is completed

and/or the subject is stabilized. If a subject has an infusion reaction with nivolumab, the lirilumab, ipilimumab, or placebo for lirilumab infusion can be given (without prophylactic medications) if the infusion reaction resolves within 3 hours. For scheduling purposes after a nivolumab infusion reaction, the lirilumab, ipilimumab, or placebo for lirilumab infusion may be given the next day. Prophylactic pre-infusion medications should be given prior to all subsequent nivolumab infusions.

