4.8.3 Definition of Non-hematologic DLT

Any of the following events will be considered a non-hematologic DLT:

- Grade 2 eye pain or reduction in visual acuity that requires systemic treatment
- Grade 2 eye pain or reduction in visual acuity that does not respond to topical therapy and that does not improve to Grade 1 within 2 weeks of initiation of topical therapy
- Grade 3 non-hepatic or non-hematologic toxicity, with the following exceptions:

The following Grade 3 non-hematologic events **will not** be considered DLTs:

- Grade 3 electrolyte abnormality that lasts less than 72 hours, is not clinically complicated, and resolves spontaneously or responds to conventional medical intervention
- Grade 3 increase in amylase or lipase that is not associated with clinical or radiographic evidence of pancreatitis
- Grade 3 nausea or vomiting that lasts less than 48 hours, and resolves to Grade 1 or less, either spontaneously or with conventional medical intervention
- Grade 3 fever that lasts less than 72 hours, and is not associated with hemodynamic compromise (including hypotension, or clinical or laboratory evidence of end organ perfusion impairment)
- Grade 3 endocrinopathy that is well controlled by hormone replacement
- Grade 3 tumor flare (defined as pain, irritation or rash that localizes to sites of known or suspected tumor)
- Grade 3 fatigue
- Grade 3 infusion reaction that returns to Grade 1 in less than 6 hours

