Vital Signs	X	X	X	X		
Vital signs will be obtained before the nivolumab infusion, after the nivolumab infusion, and after the lirilumab infusion.
 
If any vital sign is abnormal at the final check, the subject must be observed further for a period of time, as clinically indicated.
 
The start and stop time of the study drug infusion should be documented. If there are any new or worsening clinically significant changes since the last examination, report changes on the appropriate non-serious or serious adverse event page.
 
When slowing or restarting an infusion due to an infusion reaction, vital signs should be monitored every 15 minutes (± 5 minutes) or as directed by the investigator until the infusion is completed and/or the subject is stabilized. If a subject has an infusion reaction with nivolumab, the lirilumab infusion can be given (without prophylactic medications) if the infusion reaction resolves within 3 hours. For scheduling purposes after a nivolumab infusion reaction, the lirilumab infusion may be given the next day. Prophylactic pre-infusion medications should be given prior to all subsequent nivolumab infusions.

Electrocardiogram	X					
12-lead ECG (if performed on same day as study drug administration it is to be performed prior to dosing).
 
Not required on Cycle 1 Day 1

Table 5.1.1-2: On-treatment Procedural Outline the Dose Escalation and Dose Expansion (Part 1; Completed) and the SCCHN Cohort Expansion (Part 2; Completed) (CA223001)

Procedure	Cycles 1 to 12					Notes
	D1 (± 2 days)	D15 (± 2 days)	D29 (± 2 days)	D43 (± 2 days)	D49 to 56	
Chest Radiograph						As clinically indicated.
Oxygen Saturation Levels	X	X	X	X		Collected at rest prior to dosing.
Laboratory Tests	X	X	X	X		On-study laboratory tests (including pregnancy testing) to be done on site/local. Within 72 hours of re-dosing to include CBC with differential, LFTs (to include a minimum of AST, ALT, alkaline phosphatase, total bilirubin, and LDH), BUN, creatinine, glucose, Ca, Mg, Na, K, carbon dioxide, Cl, phosphorous, amylase, and lipase. Results should be examined by the investigator or appropriate designee prior to dose administration. (Subjects with HCC only, PT, PTT, INR, and fibrinogen) CBC with differential should also be collected at each timepoint where samples for immunophenotyping are collected as listed in Table 5.7.3.3-1 , Table 5.7.3.3-3 , and Table 5.7.3.3-4 .
Child-Pugh Score	X					HCC only.

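### Section 3.6 lets the second drug be given after a nivolumab infusion reaction of any grade, which the Section 4.9.5 stopping rule does not allow for Grade 3-4; practical size is low

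*Protocol*

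**What the plan says.** **Section 3.6, after the Grade 3/4 instructions.** If a subject reacts to nivolumab, the lirilumab, ipilimumab or placebo "infusion can be given (without prophylactic medications) if the infusion reaction resolves within 3 hours". The next sentence says that, for scheduling, the same second "infusion may be given the next day". Neither sentence names a grade, and the next-day sentence does not require the reaction to have resolved.

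**Section 3.6, Grade 3/4 block.** The only stopping instruction is "Nivolumab will be permanently discontinued". The block does not mention lirilumab, ipilimumab or placebo, and nothing in Section 3.6 refers to Section 4.9.5.

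**Table 5.1.1-2 (Parts 1 and 2), Vital Signs note.** This repeats both permissions for lirilumab, again without a grade: "the lirilumab infusion can be given (without prophylactic medications) if the infusion reaction resolves within 3 hours". The corresponding notes for Parts 3 and 5 do not repeat them, but Section 3.6 covers those parts.

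**Section 4.9.5.** The lead-in makes permanent discontinuation of every study drug a requirement for the events listed. These include a drug-related Grade 3 infusion reaction regardless of how long it lasts (item 2a for Parts 1 to 3, item 3a for Part 5) and any drug-related Grade 4 event (item 4). None of the exceptions under item 4 concerns infusion reactions. Section 3.5 makes these criteria mandatory.

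**The concern.** One event, a drug-related Grade 3-4 reaction to nivolumab on a day when a second infusion is due, gets two answers. Section 3.6 is what site staff would consult at the chair. It tells them to stop nivolumab and, read literally, allows the second antibody later that day without premedication, or the next day. Section 4.9.5 tells them to stop everything. A reader who uses Section 3.6 alone is never sent to the rule that should decide the matter.

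What is at stake is the safety of a few subjects, since the permitted dose would follow a severe reaction. No sample size, power or error rate is affected. The wording still matters because Revised Protocol 12 closes enrollment but lets subjects with continuing benefit stay on treatment.

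**Working it through.** **Step 1: set the two rules side by side** for a drug-related Grade 3-4 nivolumab reaction.

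| Decision | Section 3.6, read literally | Section 4.9.5 |
|---|---|---|
| Nivolumab | stop permanently | stop permanently |
| Second drug, same day | allowed if the reaction is over within 3 hours | stop permanently |
| Second drug, next day | allowed, no condition | stop permanently |

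Placebo is covered as well: Section 4.1.1 lists it as an investigational product, and Section 4 counts all such products as study drug.

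**Step 2: ask whether the 3-hour condition excludes Grade 3-4 by itself.** It narrows the route, because Section 3.6 describes Grade 3 as prolonged. It does not close it:
- The same description also includes "recurrence of symptoms following initial improvement", which is not a statement about total duration.
- Grade 4 is described by severity and the support needed, not by duration.
- Section 4.8.3 recognises a "Grade 3 infusion reaction that returns to Grade 1 in less than 6 hours". That section no longer applies, and returning to Grade 1 within 6 hours is not the same as resolving within 3. It shows only that the protocol's authors expected some Grade 3 reactions to settle within hours.

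The next-day sentence has no such filter, so the inconsistency does not depend on this step.

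**Step 3: ask whether Section 4.9.5 lets the second drug continue.** Its separate-assessment paragraph runs one way: nivolumab may go on when lirilumab and/or ipilimumab is stopped. The reverse is not stated. The closing sentence stops all drugs when the event cannot be tied to a single drug, and this leaves some room to infer the reverse. Nothing grants it expressly.

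**Step 4: size.** The inputs come from Section 1 of the protocol (combination experience, cut-off 13-Jul-2017; the SAP repeats them): 322 subjects treated, 43 with a related infusion reaction of any grade, and 4 with an infusion reaction listed directly after the count of related Grade 3-4 events.
- Stated figure reproduced: 4/322 = 0.0124 = 1.2%.
- Grade check: the 4 are not labelled Grade 3-4 in their own sentence. The any-grade count in the same paragraph is 43 (43/322 = 13.4%), so reading the 4 as the Grade 3-4 subset is the reasonable inference.
- Exact (Clopper-Pearson) 95% interval for 4/322: the lower limit is the 2.5% quantile of Beta(4, 319) = 0.34%; the upper limit is the 97.5% quantile of Beta(5, 318) = 3.15%.
- Conflict scenario: the reaction must be to nivolumab, before a second infusion that is due and, for the same-day route, over within 3 hours. The documents do not split the 4 this way. The count is therefore between 0 and 4 of 322, or 0% to 1.2%.

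Sections 1.4.13.3 (159 subjects, August 2016) and 1.4.17.2 describe combination infusion reactions as Grade 1-2 only and mainly with the first infusion. That does not match the 4 in Section 1. The Section 1 data are from a later cut than Section 1.4.13.3. Both accounts support a small size.

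**The case against.** The case on the other side is substantial.

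1. **Context.** The paragraph holding the permissions opens with slowing or restarting an infusion and ends with "Prophylactic pre-infusion medications should be given prior to all subsequent nivolumab infusions". After a Grade 3-4 reaction there is no restart and no later nivolumab infusion, so the paragraph makes full sense only for Grade 1-2. This stands as evidence of intent, but the intended limit is not written.
2. **Priority.** Section 3.6 offers recommendations that "may be modified based on local treatment standards and guidelines as appropriate", and the permissions themselves are only permissive. Section 3.5 makes the Section 4.9.5 criteria mandatory, and Section 4.9.4 leaves further dosing to the investigator only when those criteria are not met. This stands: Section 4.9.5 should govern. It shows how the conflict resolves, not that it is absent.
3. **Safeguards.** Section 4.9.5 requires details to go to health authorities in advance if treatment is to be re-initiated after a permanent-discontinuation event. Section 3.6 sends Grade 3-4 reactions to the Medical Monitor within 24 hours. Both stand. The second is a partial check, because a next-day infusion can fall inside the same 24 hours.
4. **Little exposure remains.** Enrollment is closed and most reactions came early. This stands.

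A reader might go further in three ways that the documents do not support:
- That subjects were in fact dosed against the stopping rule. No such case is reported, and the range starts at 0.
- That Section 4.9.5 settles beyond argument that lirilumab or ipilimumab must stop after a reaction clearly due to nivolumab alone. Its lead-in points that way, but its closing sentence leaves some room.
- That a count can be projected from the nivolumab lung-cancer study in Section 1.4.17.1. Its Grade 3-4 totals are for a composite category. The two events in the 30-minute group were one anaphylaxis and one bronchospasm, and the infusion-related-reaction row shows none. The categories differ, so no projection is made here.

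**Conclusion.** Wrong as written, with low magnitude. Section 3.6, and its copy in Table 5.1.1-2, contain a safety permission without a grade limit that is wider than the mandatory stopping rule in Section 4.9.5. The Grade 3/4 block of Section 3.6 adds to the problem by naming only nivolumab and giving no cross-reference.

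The number of subjects who could have met the conflict is unknown, between 0 and 4 of the 322 treated by 13-Jul-2017. This bound rests on reading the 4 reactions as Grade 3-4 and applies to that data cut only. The conclusion about the text rests on the literal wording of the two sections. It does not assume that any site read Section 3.6 that way, and it accepts that Grade 1-2 was probably intended. The correction should be made, but it is not urgent enough to bear on the trial's conclusions.

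**What to change.** Make two edits:

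1. Insert *Grade 1-2* before the reference to the infusion reaction in both permission sentences of Section 3.6, and in both sentences of the Vital Signs note in Table 5.1.1-2.
2. Add to the Grade 3/4 block of Section 3.6: *for lirilumab, ipilimumab and placebo, apply Section 4.9.5 before any further dosing.*

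The second edit deliberately points to Section 4.9.5 and does not forbid all further study drug in Section 3.6. A flat prohibition there would settle the drug-by-drug question that Section 4.9.5 leaves partly open; if the sponsor wants that settled, Section 4.9.5 is the place to do it.

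The cost is close to nothing: one phrase in each of four sentences and one added sentence, which can go into the next protocol revision with a note to sites. No analysis, sample size or data collection changes.

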3.7 Post-treatment Study Follow-up

Overall survival data will no longer be collected with Revised Protocol 12.

In this study, OS is a secondary endpoint for the SCCHN Randomized Cohorts (Part 3) [REDACTED]. Post-study follow-up is of critical importance and is essential to preserving subject safety and the integrity of the study. Subjects who discontinue study drug must continue to be followed for collection of outcome and/or survival follow-up data as required and in line with [Section 4.9.5](#) until death or the conclusion of the study.

BMS may request that survival data be collected on all treated/randomized subjects outside of the protocol-defined window (see [Section 5.1](#)). At the time of this request, each subject will be contacted to determine their survival status unless the subject has withdrawn consent for all contacts or is lost to follow-up.

3.7.1 Withdrawal of Consent

Subjects who request to discontinue study drug will remain in the study and must continue to be followed for protocol-specified follow-up procedures. The only exception to this is when a subject specifically withdraws consent for any further contact with him/her or persons previously authorized by subject to provide this information. Subjects should notify the investigator of the decision to withdraw consent from future follow-up **in writing** whenever possible. The withdrawal of consent should be explained in detail in the medical records by the investigator as to whether the withdrawal is from further treatment with study drug only or also from study procedures and/or post-treatment study follow-up; the information should be entered on the appropriate CRF page. In the event that vital status (whether the subject is alive or dead) is being measured, publicly available information should be used to determine vital status only as appropriately directed in accordance with local law.

3.7.2 Lost to Follow-Up

All reasonable efforts must be made to locate subjects to determine and report their ongoing status. This includes follow-up with persons authorized by the subject as noted above. Lost to follow-up is defined by the inability to reach the subject after a minimum of 3 documented phone calls, faxes, or emails as well as lack of response by subject to 1 registered mail letter. All attempts should be documented in the subject's medical records. If it is determined that the subject has died, the study site will use permissible local methods to obtain the date and cause of death.

If investigator's use of a third-party representative to assist in the follow-up portion of the study has been included in the subject's informed consent, then the investigator may use a BMS-retained third-party representative to assist study site staff with obtaining subject's contact information or

other public vital status data necessary to complete the follow-up portion of the study. If, after all attempts, the subject remains lost to follow-up, then the last known alive date as determined by the investigator should be reported and documented in the subject’s medical records.

4 TREATMENTS

All protocol-specified investigational and non-investigational products are considered study drug.

4.1 Study Treatments

The study drugs include lirilumab (BMS-986015), nivolumab (BMS-936558), and ipilimumab (BMS-734016). Table 4.1-1 below indicates the Dose Level to be used for each panel in the Dose Escalation and Cohort Expansion (Part 1; Completed). The placebo for lirilumab injection is normal saline injection, which is administered in a similar fashion as described for the lirilumab injection. The normal saline to use as placebo will not be provided by the Sponsor.

Table 4.1-1: Treatment Administration (Dose Escalation and Cohort Expansion [Part 1; Completed])

Dose Level	Lirilumab	Nivolumab
1	0.1 mg/kg	3 mg/kg
2	0.3 mg/kg	3 mg/kg
3	1 mg/kg	3 mg/kg
4	3 mg/kg	3 mg/kg

Product description and storage information is described in [Table 4.1-2](#).

Cohort expansions will be treated at the highest tested dose or a different Dose Level as selected by the Sponsor.

The Dose Escalation and Cohort Expansion (Part 1; completed), and the SCCHN Cohort Expansion (Part 2; completed): For treatment visits where both lirilumab and nivolumab are administered, nivolumab will be administered first followed by lirilumab. Nivolumab will be administered as a 60-minute infusion; 30 minutes after completion of the nivolumab infusion, lirilumab will be administered as a 60-minute infusion.

The SCCHN Randomized Cohorts (Part 3) (Arm A): For treatment visits where both lirilumab and nivolumab are administered, nivolumab will be administered first followed by lirilumab. Nivolumab will be administered as a 30-minute infusion; 30 minutes after completion of the nivolumab infusion, lirilumab will be administered as a 60-minute infusion.

The SCCHN Randomized Cohorts (Part 3) (Arm B): For treatment visits where both placebo for lirilumab and nivolumab are administered, nivolumab will be administered first followed by placebo for lirilumab. Nivolumab will be administered as a 30-minute infusion; 30 minutes after completion of the nivolumab infusion, placebo for lirilumab will be administered as a 60-minute infusion.

The Signal Detection in SCCHN with Lirilumab, Nivolumab, and Ipilimumab Combination (Part 5): On days when all 3 study drugs are given, nivolumab will be given first followed by ipilimumab followed by lirilumab. Nivolumab will be administered as a 30-minute infusion; 30 minutes after completion of the nivolumab infusion, ipilimumab will be administered as a 30-minute infusion; and 30 minutes after completion of the ipilimumab infusion, lirilumab will be administered as a 60-minute infusion. On days when nivolumab and lirilumab are given, nivolumab will be given first followed by lirilumab. Nivolumab will be administered as a 30-minute infusion; 30 minutes after completion of the nivolumab infusion, lirilumab will be administered as a 60-minute infusion.

Detailed administration instructions will be provided separately via study site training materials and Dosing Procedure Manual.

Table 4.1-2: Product Description and Dosage Form

Product Description and Dosage Form	Potency	Primary Packaging (Volume)/Label Type	Secondary Packaging (Qty)/Label Type	Appearance	Storage Conditions (Per Label)
BMS-986015-01 Solution for Injection, 50 mg/vial (10 mg/mL) ^a	10 mg/mL	5-mL vial/open	Box/open	Clear to opalescent, colorless liquid. Essentially free of particles.	Store at 2°C to 8°C (36°F to 46°F) protect from light, protect from freezing
BMS-986015-01 Solution for Injection, 100 mg/vial (10 mg/mL) ^a	10 mg/mL	10-mL vial/open	Box/open	Clear to opalescent, colorless liquid. Essentially free of visible particles.	Store at 2°C to 8°C (36°F to 46°F), protect from light, protect from freezing
BMS-936558-01 Solution for Injection, 40 mg/vial (10 mg/mL) ^b	10 mg/mL	10-mL vial/open	Box/open (as kit containing 2×100 mg vials BMS-936558-01 with 1× 40 mg vial)	Clear to opalescent, colorless to pale yellow liquid, light (few) particulates may be present.	Store at 2°C to 8°C (36°F to 46°F), Do not freeze. Protect from light.
BMS-936558-01 Solution for Injection, 10 mg/mL, 10 mL (100 mg/vial) ^b	10 mg/mL	10-mL vial/open	Box/open OR Box/open (as kit containing 2×100 mg vials with 1× 40 mg vial BMS-936558-01)	Clear to opalescent, colorless to pale yellow liquid, light (few) particulates may be present	Store 2°C to 8°C (36°F to 46°F); protect from light; protect from freezing.
Ipilimumab Solution for Injection, 5 mg/mL, 40mL (200 mg/vial) ^c	5 mg/mL	50-mL vial/open	Box/open	Clear to slightly opalescent, colorless to pale yellow liquid. Light (few) particulates may be present	Store 2°C to 8°C. Store in original package. Do not freeze. Protect from light.

^a BMS-986015-01 is also referred to as lirilumab.

^b BMS-936558-01 is also referred to as nivolumab.

^c BMS-734016 is also referred to as ipilimumab.

Solutions used as placebo (Normal Saline, ie, 0.9% Sodium Chloride Injection) should be sourced by investigative sites if available and permitted by local regulations. Storage should be in accordance with the product label.

